4.1 Primary safety endpoints

The primary safety endpoints include premature discontinuations of study treatment, serious adverse events and all adverse events. For more details on the analysis of the safety data, see Section 12 of this SAP.

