4.2 Primary efficacy endpoint

The primary endpoint of this study is the rate of disability progression, assessed with Area Under the Curve (AUC) of the CombiWISE scores during the 2-year treatment period. The CombiWISE data collected during the 1-year pre-treatment period will be utilized by including both the pre-treatment disability progression (AUC of CombiWISE scores during the pre-treatment period) and severity of the disability (CombiWISE score at pre-randomization baseline) as covariates in the statistical analysis.

Derivation of CombiWISE scores

CombiWISE is a combinatorial weight-adjusted disability score ranging from 0 to 100, where 0 represents no disability and 100 maximum disability. It was developed based on the pre-determined analysis of 58 candidate outcomes collected in 1 year pre-treatment phase in training (IPPOMS1) and validation (IPPOMS2 and RIVITALISE) cohorts, as described in detail in a recent publication (Kosa, Ghazali et al. 2016). The CombiWISE score is a composite of four scales: expanded disability status scale (EDSS), Scripps neurological rating scale (SNRS), 25 foot walk (25FW) and 9 hole peg test (9HPT) performed on non-dominant hand (NDH- 9HPT). The score is calculated with the following formula:

$$\begin{aligned} \text{CombiWISE} = & 33.166 + 3.803 \times \text{EDSS} - 0.407 \times \text{SNRS} + \\ & 2.409 \times \log(25\text{FW}) + 18.056 \times 25\text{FW}_{\text{fail}} + \\ & 1.305 \times \log(\text{NDH-9HPT}) + 10.751 \times \text{NDH}_{\text{fail}}. \end{aligned}$$

The components of the CombiWISE are derived as follows:

- EDSS: the EDSS score (scored as 1.0, 1.5, ..., 10.0) is recorded as such and requires no derivation.
- SNRS: the SNRS score, which can range between 100 (normal status) and 0 (worst possible score) is recorded as calculated by the investigator.
- $\log(25\text{FW})$ is \log_2 of the average of two attempts on 25FW, or 0 if at least one attempt is unsuccessful.
- $25\text{FW}_{\text{fail}}$ is 1 if patient failed either of the two attempts on 25FW; otherwise 0.
- $\log(\text{NDH-9HPT})$ is \log_2 of average of two attempts on 9HPT with non-dominant hand, or 0 if at least one attempt is unsuccessful.

- NDH_{fail} is 1 if patient failed either of the two attempts on 9HPT with non-dominant hand; otherwise 0.

Calculation of AUC values

The CombiWISE is assessed at the following time points:

- Pre-treatment baseline phase: Months -12, -6 and 0
- Double-blind phase: Months 6, 12, 18 and 24.

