The AUC values will be calculated for both the pre-treatment baseline phase (from Months -12, -6 and 0) and for the double-blind phase (from Months 0, 6, 12, 18 and 24). For each of the AUC values, at least two valid CombiWISE scores during the phase in question are required. If less than two values AUC values are available for any of the two phases, the AUC score will be set as missing. In addition, if the first value of the phase in question is missing, the CombiWISE score will be set as missing.

Linear trapezoidal method will be used to calculate the AUC values. For each time interval (time between two visits), the AUC is calculated as $0.5 \times (Y_1 + Y_2) \times (t_2 - t_1)$, where Y_1 and Y_2 are the CombiWISE scores (as changes from baseline) at the beginning and end of the interval and t_1 and t_2 are the start and stop dates of the interval. The time will be converted to years (number of days divided by 365.25) for the AUC calculation. The baseline for the pre-treatment period is the visit scheduled at the beginning of the pre-treatment period (Month -12) and the baseline for the double-blind period is the visit at Month 0.

In case of intermittent missing data between two non-missing visits, the formula for linear trapezoidal method will be used as such. In case of premature discontinuations, the AUC values after the time of discontinuation will be set as missing.

After these calculations, the AUC values calculated for the different periods will be summed over the pre-treatment baseline phase (Month -12 to Month 0) and over the double-blind phase (Month 0 to Month 24). Because the follow-up times can vary from patient to patient, the AUC values will be made comparable by scaling them using the follow-up time. The scaling will be done by dividing the AUC value by the square of the actual duration of each of the phases. For the pre-treatment baseline phase, the AUC will be scaled as $AUC/[t_0 - t_{-12}]^2$, where t_0 and t_{-12} are the dates of visits at Month 0 and Month -12, respectively. For the double-blind phase, the AUC will be scaled as $AUC/[t_{last} - t_0]^2$, where t_{last} and t_0 are the dates of the last visit and the visit at Month 0, respectively. Similarly as above, the time will be converted to years. The scaled AUCs will be used in all statistical analyses.

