The imputed datasets generated with the approach described above do contain only non-missing values and are used as input in the model for the sensitivity analysis of the primary outcome variable. Random coefficient regression models similar as described in Sensitivity Analysis 1 will thus be run on each of the 1000 generated imputed datasets and the difference between the treatment groups will be estimated. Finally, the results from these analyses will be combined to derive an overall estimate of the treatment difference. In addition to the estimates, corresponding 95% confidence intervals and p-values will be calculated.

- Multiple Imputation assuming data missing not at random (MNAR) will be done to compare idebenone to placebo. Control group based assumption (Copy Reference imputation) will be used, i.e. the trajectories of the patients are assumed to follow the placebo group trajectories after the discontinuation. Methods similar to the procedure described above will be used to generate monotone missing data. After this, the missing data will be imputed sequentially for each visit (first Month 3, followed by all subsequent visits). Only the data from the control group (placebo group) will be used as input for each imputation of both treatment groups.

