14.1 Disposition

Number of enrolled, randomized, completed and discontinued patients will be summarized. In addition, the reasons for discontinuations will be tabulated. The time to premature discontinuation will be illustrated with Kaplan-Maier plots.

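### SAP 4.2 can drop off-therapy CombiWISE scores from the ITT primary analysis and does not tie the AUC divisor to the last score summed

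*SAP*

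**What the plan says.** SAP 4.2 builds the primary endpoint from trapezoids of change from the phase baseline, sums them over the phase, and divides by the squared duration of the phase in years. The reason given is "Because the follow-up times can vary from patient to patient".

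- **What enters the sum.** Gaps between two scored visits are bridged by the trapezoid. After that: "In case of premature discontinuations, the AUC values after the time of discontinuation will be set as missing".
- **What the divisor is.** The two dates in the double-blind divisor "are the dates of the last visit and the visit at Month 0, respectively". SAP 16 describes the same scaling as being to the length of the assessment period.
- **Minimum data.** "For each of the AUC values, at least two valid CombiWISE scores during the phase in question are required".
- **Incomplete data.** SAP 13.1.1 refers to a single imputation algorithm in Section 4.2, which contains only the rules above. Protocol 11.3 replaces a missing Month 24 value by the mean of the two preceding values. SAP 4.2 does not repeat this, and the SAP takes precedence over the protocol where they differ.

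The primary ANCOVA uses the ITT population, with a secondary run in Completers. Protocol 9.3 says that patients whose treatment is stopped under the EDSS or the contrast-enhancing-lesion (CEL) criterion continue off therapy, with all outcomes collected, for intention to treat. A later paragraph of the same section gives patients who stop dosing two further months of follow-up.

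**The concern.** Two terms that decide a patient's primary score are undefined: discontinuation and last visit.

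If discontinuation means stopping treatment, scores collected for the intention-to-treat analysis do not reach it. The patients concerned were stopped because they worsened, so the missing part is not a random part.

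If the last visit can be one without a score in the AUC, numerator and denominator cover different periods. Because the denominator is squared, the patient's progression is understated more than in proportion.

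**Working it through.** **1. The plan's own factor.** Protocol 11.2 says a 2-year AUC must be divided by 4 to match a 1-year AUC. With linear progression at rate b per year, the AUC to time u is 0.5·b·u². One year gives 0.5b and two years give 2.0b, a ratio of 4. It reproduces. Dividing by u² gives 0.5b for every u, so the scaling works when sum and divisor end at the same date.

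**2. What discontinuation can mean.**

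| Place | Use | Fits |
|---|---|---|
| SAP 4.1 | "The primary safety endpoints include premature discontinuations of study treatment, serious adverse events and all adverse events" | stopping treatment |
| SAP 13.1.2 | "the trajectories of the patients are assumed to follow the placebo group trajectories after the discontinuation" | leaving the study |
| SAP 14.1 | "Number of enrolled, randomized, completed and discontinued patients will be summarized" | leaving the study |

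If it means leaving the study, no later scores exist and nothing is lost. If it means stopping treatment, the off-therapy scores from the two MS safety criteria are dropped. Protocol 7.5.3 calls true CEL extremely rare, so in practice this is the EDSS criterion: worsening of more than 2 points, confirmed a month later. At the average 7.50 CombiWISE points per EDSS point (Protocol 11.5), that is more than 2 × 7.50 = 15 points. Protocol 9.3 states no such collection for other reasons for stopping.

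**3. Effect of dropping those scores, divisor matched.**

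- Linear progression throughout: 0.5b either way, so no bias, but more noise. With independent error variance σ² per visit, an AUC ending at Month 6 reduces to Y6 − Y0, with variance 2.00σ². To Month 24 the weights are −0.4375, 0.125, 0.125, 0.125 and 0.0625, giving 0.1914 + 3 × 0.0156 + 0.0039 = 0.242σ².
- Rate changes after stopping (illustration: 50% slowing on drug, stop at Month 12, full rate b afterwards): changes at Months 6, 12, 18 and 24 are 0.25b, 0.5b, 1.0b and 1.5b. All scores give 1.25b/4 = 0.3125b, or 37.5% slowing against 0.5b. Scores cut at Month 12 give 0.25b, or 50%.

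**4. Effect of an unmatched divisor.** A sum to time u divided by v² gives (u/v)² of the matched score for any trajectory. If the next scheduled visit is attended but not scored:

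| Last score | Last visit | Share of matched score | Shift in the mean of an arm of 33 |
|---|---|---|---|
| Month 18 | Month 24 | (18/24)² = 56% | 0.4375/33 = 1.3% |
| Month 12 | Month 18 | (12/18)² = 44% | 0.5556/33 = 1.7% |
| Month 6 | Month 12 | (6/12)² = 25% | 0.75/33 = 2.3% |

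The last column is for one affected patient of average slope.

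If the Protocol 11.3 substitution applies, Month 24 in the first row becomes (1.0b + 1.5b)/2 = 1.25b. The last segment is 0.5 × (1.5b + 1.25b) × 0.5 = 0.6875b, and the score is (1.125b + 0.6875b)/4 = 0.453b, or 91% of 0.5b. The arm shift falls to 0.094/33 = 0.3%.

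**5. Scale.** With the planning mean 51.24 and SD 46.2 (SAP 6.2), the unadjusted standard error of a difference at 33 per arm is 46.2 × √(2/33) = 11.4, about 22% of the mean. One patient in the first row moves the comparison by 1.3/22, or 0.06 of a standard error.

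**The case against.** The best defence is context. SAP 4.2 lists the CombiWISE time points and then uses visit for the ends of AUC intervals. The stated purpose is comparability over unequal follow-up, and SAP 16 speaks of the assessment period. On that reading the divisor ends with the sum and the scaling is exact. This largely stands: a matched divisor is probably intended, but the text does not require it.

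Unscored visits should also be uncommon. "The CombiWISE score is a composite of four scales", but a failed walk or peg test still yields a score through the fail terms, so a component must be truly missing. The Completer ANCOVA, which requires valid assessments up to Month 24, is not exposed to an unscored final visit. The random-coefficient and MMRM analyses use observed scores.

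On discontinuation, the sentence directly follows the rule for intermittent gaps, which fits drop-out. That reading is open. However, the only place where the SAP names what is discontinued is SAP 4.1, and there it is study treatment.

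A reader might infer that patients who stop early routinely have their AUC divided by the full two years, leaving (6/24)² = 6% or (12/24)² = 25% of their score. That needs both the treatment reading and the literal divisor, against the context just described. A reader might also infer bias towards one arm. The documents give no counts by arm of treatment stops or unscored visits, so they support neither a direction nor a total effect.

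**Conclusion.** The point holds in two parts, with medium confidence, and should be fixed.

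First, under the treatment reading the ITT primary ANCOVA leaves out scores the protocol says are collected for it, in a small group selected by worsening. This remains true with a matched divisor. The change in estimate depends on how patients progress after stopping: none on average if progression stays linear.

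Second, the divisor's end date is not defined. Where it outruns the sum, the score is understated by the squared ratio, for example to 56%, or to about 91% if the Month 24 substitution survives. Whether it survives is unclear: SAP 4.2 omits it and the SAP takes precedence, yet SAP 16 lists only the scaling as a change to the primary analysis.

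Each affected patient moves the comparison little against the planning noise. Nothing here shows that the reported result is wrong. Protocol 7.6 says the analysis is complete, but the documents do not say which rule was programmed.

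**What to change.** In SAP 4.2, by addendum:

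1. Replace the set-as-missing sentence with: *every observed CombiWISE score up to Month 24 enters the AUC regardless of treatment status.*
2. Define t_last as the date of the last CombiWISE score in the AUC.
3. State whether the Month 24 substitution in Protocol 11.3 applies to the primary AUC.

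The two statements in Protocol 9.3 on follow-up after stopping must be reconciled, because they determine which off-therapy scores should exist.

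Since the analysis is reported complete, state which rule was programmed and compare, for each patient, the last attended visit with the last score used. Rerun the primary ANCOVA only if off-treatment scores were dropped or sum and divisor did not match.

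The cost is a short addendum, a check of two dates per patient, and at most one rerun on data already collected. The small downside is that the estimate then includes off-treatment time, as the protocol's intention-to-treat follow-up already implies.

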4.3 Secondary efficacy endpoints

All components of the primary endpoint will be analyzed as secondary endpoints:

- EDSS: the EDSS score (scored as 1.0, 1.5, ..., 10.0) is recorded as such and requires no derivation.

-
- SNRS: the SNRS score, which can range between 100 (normal status) and 0 (worst possible score) is recorded as calculated by the investigator.
 - 25 foot walk (25FW): 25FW is the average of two attempts of walk test. In case any of the two attempts is unsuccessful, 25FW will be set as missing. This endpoint will be primarily analyzed without any transformation to facilitate the interpretation, but in case the data are skewed, additional analyses may be conducted by log2 transformation of the average.
 - 9 hole peg test (9HPT) performed on non-dominant hand (NDH-9HPT): NDH-9HPT is the average of the two attempts on 9 hole peg test. In case any of the two attempts is unsuccessful, NDH-9HPT will be set as missing. This endpoint will be primarily analyzed without any transformation to facilitate the interpretation, but in case the data are skewed, additional analyses may be conducted by log2 transformation of the average. Furthermore, similar analyses will be conducted for data based on the dominant hand and the average of the non-dominant and dominant hands.

In addition, the following variables will be analyzed as secondary endpoints:

- Neuroimaging outcomes: Inhibition of individualized rates of enlargement of ventricular volume: enlargement of segmented volume of lateral and 3rd ventricles. This was the primary endpoint of the initial protocol version.
- EDSS-plus, as defined in (Cadavid, Cohen et al. 2017): EDSS-plus is defined as progression on at least 1 of 3 components (EDSS, 25FW, and/or NDH-9HPT) confirmed ≥ 24 weeks apart and with a $\geq 20\%$ minimum threshold change for 25FW and NDH-9HPT. As the visits in this study are scheduled to be conducted with 6 month intervals, a confirmation at the next scheduled visit is considered sufficient, even if the time between the visits would be less than 24 weeks due to visit scheduling.

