10.2.2 Clinical/functional outcomes

1. Progression in EDSS-plus, as defined in (Cadavid, Cohen et al. 2017). EDSS-plus response will be analyzed using a cox proportional hazards model.
2. Progression of lower extremity disability as assessed by 25 foot walk component of MSFC
3. Progression of upper extremity/fine motor movements disability as assessed by non-dominant hand 9 hole peg test component of MSFC
4. Progression of neurological disability as assessed by Scripps NRS
5. Progression of neurological disability as assessed by EDSS

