11.3 Handling of missing/unobtainable data

All efforts will be made to collect a complete set of data by employing 1-2 week flexibility in scheduling and repeating inadequate quality MRI scans.

With the exception of the primary endpoint (AUCs) and the sensitivity analyses, for continuous and categorical endpoints, no data imputation will be made and missing data will be handled by the models itself.

The following single imputation method is applicable for handling of missing data to calculate AUCs of CombiWISE scores and MRI data.

If particular data points are missing for reasons other than inability to perform the test (i.e. because of disability) we will replace the missing data according to following algorithm:

- a. For data obtained every 6 months (i.e. clinical data and brain MRI data), the missing time point will be substituted by the average of 2 adjacent time-points: i.e. 6 months before and 6 months after the missing time-point. If the last time-point is missing (i.e. month 24), we will substitute the data for this time-point by the average of 2 preceding time-points.
- b. For data obtained once at baseline and once at treatment phase (i.e. CSF), the missing data cannot be replaced and the patient will be eliminated from analysis.

Handling data missing because the patient was unable to perform the test due to disability: this may happen for clinical tests such as timed 25 foot walk (25FW), 9 hole peg test (9HPT) and PASAT. These data will be calculated using the following recommendations from scoring instructions for the MSFC:

- a. 25FW: the inability to perform 25FW will be substituted by the largest Z-score in the MSFC Task force database (i.e. with the slowest time of any patient in the combined dataset used by the Task Force in its published meta-analysis). The largest Z-score in the Task Force dataset is 13.7, therefore, for a subject who could not complete the 25FW $Z_{leg, average} = -13.7$ will be used.
- b. 9HPT: the inability to perform 9HPT will be coded as 777 and the following Z-score calculation formula will be applied:

$$Z_{arm, trial\#} = [(1/777 - \text{Baseline mean (1/9HPT)}) / \text{Baseline SD (1/9HPT)}]$$
- c. PASAT: In the event an individual patient cannot complete PASAT-3 due to disability, a score of 0 will be assigned.

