13.2 Secondary Endpoints

Continuous secondary endpoints (other than the neuroimaging outcomes) will be analyzed using random coefficient regression models similar to the one defined above for the primary outcome variable. In addition, analyses using MMRM will be conducted as well, in order to estimate the treatment differences separately at each visit. The neuroimaging outcomes will be analyzed by calculating AUC values and using ANCOVA models, similar to the primary analysis.

Categorical time-to-event endpoints (EDSS-plus) will be analyzed using Cox Proportional hazards models, with treatment group as a covariate. The patients who do not have an event during the study will be censored at the time of the last assessment of EDSS-plus. The exact number of days from the date of first dose to date of event or censoring will be used as endpoint.

The ITT population will be used for the analysis of the secondary endpoints.

14 Analysis of safety

The safety analyses will be conducted for the following study periods and treatment groups:

- Pre-treatment baseline phase: untreated patients, classified by the treatment group in the double-blind phase and overall
- Double-blind phase: Idebenone treated patients versus placebo treated patients

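### The stand-alone 25-foot walk and non-dominant peg test drop any visit with a failed attempt, while CombiWISE scores the same failure as worsening, and no sensitivity analysis covers the gap

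*SAP*

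**What the plan says.** **Stand-alone endpoints (SAP 4.3).** For the walk: "In case any of the two attempts is unsuccessful, 25FW will be set as missing". For the peg test: "In case any of the two attempts is unsuccessful, NDH-9HPT will be set as missing". Both are analysed primarily in untransformed seconds.

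**CombiWISE (SAP 4.2).** The walk-failure indicator "is 1 if patient failed either of the two attempts on 25FW; otherwise 0". The peg-test indicator works the same way. On failure the log-time term becomes 0 and a fixed penalty is added, on a scale where higher is worse.

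**Models (SAP 13.2).** Continuous secondary endpoints other than neuroimaging "will be analyzed using random coefficient regression models similar to the one defined above for the primary outcome variable", with MMRM in addition. The multiple-imputation analyses in SAP 13.1.2, including the missing-not-at-random one, are for CombiWISE only.

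**Protocol 11.3.** Outside the primary AUCs and the sensitivity analyses, "no data imputation will be made and missing data will be handled by the models itself". The same section then deals separately with inability due to disability, noting that "this may happen for clinical tests such as timed 25 foot walk (25FW), 9 hole peg test (9HPT) and PASAT". For the walk, "the inability to perform 25FW will be substituted by the largest Z-score in the MSFC Task force database"; for the peg test a code of 777 enters the Z-score formula.

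**Protocol 10.2.2.** The walk endpoint is described as "Progression of lower extremity disability as assessed by 25 foot walk component of MSFC", and the peg-test endpoint in the same way.

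**The concern.** One trigger, failure of either of two attempts, has opposite consequences in adjoining sections of the SAP. The primary score counts it as worsening. The stand-alone endpoints, which SAP 4.3 presents as components of that score, delete the visit.

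The deletion is caused by the outcome when a patient fails because walking or hand function has been lost. The planned mixed models are valid if the gap is explained by observed data, and here it depends on the value that could not be observed. SAP 13.1.2 plans a missing-not-at-random analysis for CombiWISE, where a failed test leaves no gap, but none is planned for the two endpoints where it does. A reader of the results could not tell a stable walking time from one where patients who lost the walk have left the data.

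A patient who fails at Month 0 would also leave any model that uses the Month 0 value of that test as a covariate.

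**Working it through.** **1. What a failure is worth in CombiWISE.** From the SAP 4.2 formula, going from a timed result of s seconds to a failure changes the score by:
- walk: 18.056 − 2.409 × log2(s). From 10 s, +10.05; from 30 s, +6.24; from 60 s, +3.83. Break-even is 2^(18.056/2.409) = 180.4 s.
- peg test: 10.751 − 1.305 × log2(s). From 30 s, +4.35; from 60 s, +3.04. Break-even is 2^(10.751/1.305) = 302.0 s.

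A new failure is thus scored as worsening unless the earlier time exceeded about 180 s or 302 s. The stand-alone endpoint records nothing at that visit.

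**2. What one patient's data look like (illustrative times, Months 0 to 24, F = failed).**
- 12, 15, F, 18, 20 s: only one visit is lost. Least squares on the other four gives 3.8 s/year.
- 25, 30, 36, F, F s: three visits remain, with slope 11 s/year. The fitted Month 24 value is 30.33 + 11 × 1.5 = 46.8 s, for a patient who cannot do the test.

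**3. Can failure be foreseen?** Protocol 11.3 says so. How often is unclear. Protocol 6.1 admits patients up to EDSS 7. The scale in protocol 23.4.1 limits walking at 7.0 to about 5 m even with aid, and 25 ft × 0.3048 = 7.62 m. Protocol 4.7 and the eligibility checklist (25.2) describe EDSS 7 as ambulatory with bilateral support, and 4.7 excludes non-ambulatory patients. Walk failure at entry is possible but not certain.

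**4. Effect on the treatment comparison when failure means a time beyond a common limit.** All inputs are assumed: log2 time with intercept SD 1; mean slope 0.4/year on placebo and 0.2/year on idebenone; (slope SD, residual SD) of (0.5, 0.2), (0.5, 0.4) or (0.8, 0.4); Month 0 failures excluded; MMRM with unstructured covariance. Loss is the percentage by which the Month 24 effect shrinks against the same data without gaps.

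Adjusting for Month 0 only (60,000 per arm):

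| Placebo failures | Loss |
|---|---|
| 6% | 2.4-5.5% |
| 10% | 4.2-8.4% |
| 18-19% | 8.6-16.3% |
| 26-28% | 12.9-23.1% |

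Adding Months −12 and −6 as covariates (40,000 per arm, baseline mean 3.3, separately chosen limits):

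| Placebo failures | Month 0 only | With Months −12 and −6 |
|---|---|---|
| about 10% | 3.5%; 10.0% | 2.1%; 8.3% |
| about 25% | 12.3%; 21.7%; 17.8% | 7.6%; 18.1%; 12.3% |

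The second table is closer to the plan, because the random-coefficient model uses the pre-treatment visits and the MMRM in SAP 13.1.2 adjusts for the pre-treatment slope. Neither table fits the random-coefficient model itself, and both work in log2 time rather than seconds.

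**5. Treatment only prevents failure and completed times are alike.** The completed-visit difference is then zero by construction. With failures tied at the worst rank, the probability that an idebenone patient does better is 0.5 + 0.5 × (placebo failure rate − idebenone failure rate): 0.525 for 10% v 5%, 0.55 for 20% v 10%, 0.575 for 30% v 15%. These rates are illustrative.

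**6. No drug effect.** Simple Month 24 means of completed tests at 33 per arm, with assumed limits of 60, 120 and 180 s, differ between arms by −0.05, −0.02 and 0.07 s when failures are dropped. They differ by −0.04, −0.05 and 0.05 s when failures are scored at the limit. Neither rule creates a difference.

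**The case against.** **Loss of function is counted elsewhere.** CombiWISE scores it, and EDSS and SNRS are separate secondary endpoints. Time in seconds among completed tests is a legitimate, narrower question, and the SAP says it chose seconds to ease interpretation. This stands as a reason to keep the seconds analysis. It does not remove the need to say that the analysis covers completed tests only, or to show what was left out.

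**A reader might infer that the SAP breaches protocol 11.3.** That is arguable, and the documents do not settle it. The no-imputation sentence supports the SAP. The worst scores are MSFC scoring conventions that do not carry over to seconds, and they cover inability due to disability, whereas the SAP rule covers any unsuccessful attempt. Against this, 11.3 keeps inability apart from other missing data and names both tests, and 10.2.2 calls both endpoints MSFC components.

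**A reader might infer that nobody at EDSS 7.0 can have a walk time.** Only the scale in 23.4.1 supports that; 4.7 and 25.2 point the other way.

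**A reader might infer that EDSS-plus is damaged too.** SAP 4.3 defines it by a cited publication, which may carry its own rule for inability. No defect can be shown from the documents.

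**The models recover some of the loss.** They do: pre-treatment information lowers the assumed-input losses, as the second table shows, but does not remove them.

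**Conclusion.** The point holds for the two stand-alone endpoints. The SAP drops a visit that its own primary score treats as worsening, feeds the gap to models that assume missing at random, and plans no check. Loss of function is understated there, and a treatment effect on it would tend to be attenuated.

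The group-level size is unknown. Under the assumed inputs the loss of the Month 24 effect is roughly 2-8% at about 10% placebo failures and 8-18% at about 25% when pre-treatment visits are used, or about 4-8% and 13-23% with Month 0 adjustment only. Failure rates of this order have no anchor in the documents.

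No false-positive risk is shown, and the primary, EDSS and SNRS analyses are unaffected. The exploratory MSFC captures inability if it is scored under protocol 11.3. The amendment is worth making because it is cheap, not because the trial's main conclusion depends on it.

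**What to change.** In SAP 4.3 and 13.2, keep the seconds analysis, label it as applying to visits where both attempts were completed, and add text such as:

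> Failures on 25FW and NDH-9HPT will be tabulated by arm and visit, with the reason. In a pre-specified supportive analysis at Month 24, a test not completed because of disability takes the worst rank, tied, below every completed time. Failures for other reasons stay missing. Ranks are compared by ANCOVA with treatment, Month 0 rank (same rule) and baseline age.

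For EDSS-plus, state only that the set-to-missing rule in SAP 4.3 does not override the cited definition. In SAP 16, state how the handling of failed tests relates to protocol 11.3. The descriptions of EDSS 7 in protocol 4.7, 23.4.1 and 25.2 must be reconciled.

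**Cost.** SAP wording, one extra analysis per endpoint and one table. The fail indicators are already derived for CombiWISE, but they do not carry the reason for failure, which has to be taken from the records.

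**Downsides.** Ranks are harder to interpret than seconds. Patients without a Month 24 visit are not in the supportive analysis, and a patient already failing at Month 0 cannot worsen on that test. If one failed attempt of two counts as failure, as in CombiWISE, a patient who managed the other attempt is ranked with those who managed neither.
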